9.2 Mirtazapine: IMP1

In the mirtazapine group, the 'Morning' medication will contain placebo and the 'Bedtime' medication dispensed at Visit 1 will contain mirtazapine 15 mg. Thus, the subjects in this group will initially receive treatment with

- Placebo oral tablet in the morning and
- Mirtazapine 15 mg oral tablet at bedtime.

The medication dispensed at Visit 2 on day 7(+/-1) will be the same and administration will remain unchanged in week 2 if dosage increase is not desired.

If dosage increase is desired at Visit 2 the 'Morning, noon and afternoon/evening' medication will be unchanged and still contain placebo. However, the 'Bedtime' medication dispensed will contain mirtazapine 30 mg as opposed to 15 mg in week 1. Thus, the treatment in the second week will be

- Placebo oral tablet in the morning, at noon and late afternoon/early evening and
- Mirtazapine 30 mg oral tablet at bedtime.

Mirtazapine is an antidepressant known to have antiemetic and appetite-stimulating effect. It is an alfa2-receptor antagonist, an antagonist on several serotonin-receptors (5HT_{2A}, 5HT_{2C} and 5HT₃) and on one histamine-receptor (H₁).

Recommended dosage is 15-30 mg daily initially and 15-45 mg daily as maintenance dosage, preferably administered once daily before bedtime.

Peak plasma-concentration is reached within 2 hours after oral administration. Elimination half-life is 20-40hours and time to reach steady state is 3-4 days.

Side effects:

- >10% : Increased appetite, weight gain, dry mouth, headache, sedation and somnolence.
- 1-10%: Diarrhea, obstipation, vomiting, orthostatic hypotension, peripheral edema, arthralgia, myalgia, back pain, abnormal dreams, anxiety, drowsiness, confusion, dizziness, tremor and rash.
- 0,1-1%: Hypotension, agitation, hallucinations, mania, motoric unrest, paresthesia, syncope.
- 0,01-0,1%: Pancreatitis, aggressiveness, myoclonia.
- Not known: Edema, eosinophilia, bone marrow depression, hyponatremia, rhabdomyolysis, dysarthria, oral paresthesia, serotonin syndrome, suicidal thoughts or behavior, bullous dermatitis, erythema multiforme, Stevens-Johnsons syndrome, toxic epidermal necrolysis, urine-retention.(37)

There is data on 1963 mirtazapine-exposed pregnant women without higher incidence of congenital malformations(32-35).

9.3 Ondansetron: IMP2

In the ondansetron group both the 'Morning' and the 'Bedtime' medication dispensed at Visit 1 on Day 0 will contain ondansetron 8 mg. Consequentially the subjects in this group will initially receive

- Ondansetron 8 mg oral tablet in the morning and at bedtime.

If dosage increase is desired on at Visit 2 on Day 7(+/-1) the medication dosage in the dispensed medication will remain unchanged, but with the two added administrations the treatment regimen will be

- Ondansetron 8 mg oral tablet in the morning, at noon, in late afternoon/early evening and at bedtime.

Ondansetron is an antiemetic. It works as a serotonin antagonist by binding selectively to the 5HT₃-receptors in the chemo-receptors of the trigger zone thus reducing nausea and vomiting.

Recommended dosage depends is 8 mg every 12 hours.

Peak plasma-concentration is reached within 1,5 hours after oral administration, and elimination half-life is about 3 hours.

Side effects:

- >10%: Headache.
- 1-10%: Blushing, sensation of heat, obstipation.
- 0,1-1%: Affected liver, arrhythmia, bradycardia, hypotension, extrapyramidal symptoms.
- 0,01-0,1%: QT-interval prolongation, allergic reactions, anaphylactic reaction, visual disturbances (primarily seen in i.v. administration)
- <0,01%: Toxic epidermal necrolysis, passing blindness (primarily seen in i.v. administration).(45)

Obstipation is a common side effect to ondansetron and this will be emphasised at randomisation and in the folder 'Praktisk information om forsøgsmedicinen'. Patients will be encouraged to administer a laxative (we recommend magnesium) if they experience any signs of constipation.

CONFIDENTIAL

In spite of the large number of ondansetron-exposed pregnant women it is still unclear whether ondansetron caused a higher incidence of congenital heart defects. Two studies have found a higher incidence of congenital heart defects, while three studies have not(18). However, ondansetron is frequently used for HG in Denmark and other countries.

9.4 Placebo

In the placebo group both the 'Morning' and the 'Bedtime' medication dispensed at Visit 1 on Day 0 will contain placebo. Consequentially the subjects in this group will initially receive

Placebo oral tablet in the morning and at bedtime.

If dosage increase is desired on at Visit 2 on Day 7(+/-1) the medication will still be placebo, but with the added administrations the treatment regimen will be

Placebo oral tablet in the morning, at noon, in late afternoon/early evening and at bedtime.

9.5 Rescue Medication: Metoclopramide

All three groups will receive metoclopramide which they are allowed to use as rescue medication. In case of insufficient symptom relief, subjects are allowed to administer

Metoclopramide 10 mg oral tablet or i.v. max x 3 daily.

Subjects will be asked to register administered rescue medication in the daily online questionnaires.

Metoclopramide is an antiemetic that increases gastrointestinal motility. It is a competitive dopamine(D₂)-receptor antagonist and in high concentrations it also works as a 5HT₃-receptor antagonist. Furthermore, it inhibits the chemo-receptors of the trigger zone and thus reduces nausea and vomiting.

Recommended dosage is 10 mg max x3 daily.

Peak plasma-concentration is reached within 1 hour after oral administration, and elimination half-life is 3-5 hours.

Side effects:

- >10%: Drowsiness.
- 1-10%: Weakness, diarrhea, dry mouth, hypotension, akathisia, depression, extrapyramidal symptoms, parkinsonism.
- 0,1-1%: Bradycardia, hyperprolactinemia, loss of consciousness, dyskinesia, dystonia, hallucinations, hypersensitivity, amenorrhea.
- 0,01-0,1%: Confusion, cramps.
- Not Known: AV-bloc, QT-interval prolongation, cardiac arrest, hypertension, vascular collapse, methemoglobinemia, gynecomastia, malignant neuroleptica syndrome, suicidal behavior, syncope, tardive dyskinesia, allergic reactions.(46)

Subjects will be thoroughly instructed to stop administrations of metoclopramide if they experience extrapyramidal symptoms.

9.6 Thiamine

All subjects will receive treatment with thiamine during the trial as to minimize the risk of developing Wernicke's encephalopathy. If the subject is hospitalised thiamine 100 mg i.v. will be administered daily. Out-patient participants will take 1 oral tablet Apovit B-combin stærk daily which contains B1 15 mg, B2 15 mg and B6 15 mg.

9.7 IMP Management and accountability

At each study site, there will be an IMP accountability log that will contain

- Amount received at the study site
- Date of delivery
- Expiration date
- Amount accessible at the study site
- Date and initials of the person updating the log

There will be an accountability log on subject level to ensure traceability and compliance. This log will contain

- Subject ID

CONFIDENTIAL

- Expiration date
- Amount dispensed
- Dispensed by: date and initials
- Amount returned by subject
- Excess medication received by

The subjects will be instructed to keep a log of administered IMP and rescue medication as described in the folder 'Praktisk information om forsøgsmedicinen'. They will be asked to return any unused medication. The local investigators are responsible for keeping the accountability log up to date at centre level as well as on subject level.

IMP management and accountability will be monitored by the GCP-unit throughout the trial.

10. Procedures

10.1 Visit Schedule

Visit ID	Procedures to be performed at the visit
Screening Visit Day -2-0	Obtain written informed consent for the trial before any other trial procedures are performed Assess compliance with inclusion and exclusion criteria Obtain demographic data Record medical history Record use of relevant previous medications and concomitant medication Record PUQE-24 score Record pre-pregnancy weight Measure weight Measure height Measure vital signs Perform physical examination Perform ultrasound scan to confirm gestational age and singleton pregnancy, if there is no record of such in the medical journal from within 4 four weeks prior to visit Collect blood samples Record ECG to rule out long QT-syndrome Schedule date for next visit.
Visit 1 (Randomisation) Day 0 Baseline values recorded	Re-assess compliance with inclusion and exclusion criteria Record changes to concomitant medication Record PUQE-24 score Record nausea VAS Record number of daily vomiting Record EQ-5D, NVPQOL, HELP and modified PSQI Record possible patient consideration of termination of pregnancy Measure weight Measure vital signs Collect blood samples Randomise the subject Instruct the subject on how to use the IMP Dispense IMP, rescue medication and B-kombin to the subject (sufficient medication for 10 days) Schedule date for next visit
Visit 2 Day 7	Re-assess compliance with inclusion and exclusion criteria Record changes to concomitant medication and including rescue medication Record PUQE-24 score Record nausea VAS Record number of daily vomiting Record EQ-5D, NVPQOL, HELP and modified PSQI

CONFIDENTIAL

Visit ID	Procedures to be performed at the visit
	Record patient satisfaction with treatment VAS Record possible patient consideration of termination of pregnancy Record sick leave Record possible hospitalization Record possible administration of i.v. fluids Record side effects Assess AEs occurring since the last visit Record use of rescue medication Record desire for dosage increase Measure weight Measure vital signs Record ECG Collect blood samples Collect used IMP and rescue medication and perform drug accountability and compliance check Dispense IMP, rescue medication and B-kombin to the subject (sufficient medication for 10 days) Schedule date for next visit
Visit 3 Day 14	Re-assess compliance with inclusion and exclusion criteria Record changes to concomitant medication including rescue medication Record PQUE-24 score Record nausea VAS Record number of daily vomiting Record EQ-5D, NVPQOL, HELP and modified PSQI Record patient satisfaction with treatment VAS Record possible patient consideration of termination of pregnancy Record sick leave Record possible hospitalization Record possible administration of i.v. fluids Record side effects Assess AEs occurring since the last visit Record use of rescue medication Record desire to continue trial medication Measure weight Measure vital signs Record ECG Collect blood samples Collect used IMP and rescue medication and perform drug accountability and compliance check If continuous treatment is desired the subject will be unblinded
Pregnancy Outcome obtained from Medical Journal	Record gestational age at birth or loss/termination of pregnancy Record APGAR Record gender Record birth weight Record umbilical cord pH Record placenta weight Record possible congenital malformations and hospitalization at neonatal ward during the first month post-partum

10.2 Trial Procedures

This section outlines the trial procedures that will be performed during the trial. For further details on the specific timing of the procedures please refer to the visit schedule in above.

The tasks listed below must be performed by a physician or an appropriately trained nurse or midwife to whom the local investigator has delegated the tasks:

CONFIDENTIAL

- Obtainment of informed consent
- Evaluation of in- and exclusion criteria
- Physical examination
- Assessment of AEs/SAEs
- Assessment of ECG and other laboratory results
- Decision to break the randomisation code for individual subjects (See **7.3 Discontinuation** and **8.2 Blinding**)

10.3 Informed Consent

The written informed consent must be obtained (i.e. signed and dated by the subject) before any trial activities are performed.

Each subject must be informed that participation in the trial is voluntary and that he/she may withdraw from the trial at any time during the course of the trial and that withdrawal of consent will not affect his/her subsequent medical treatment or relationship with the treating physician.

Subjects meeting the inclusion criteria for the trial will be given thorough verbal and written information about the trial. This information will be given by a trial authorized physician, nurse or midwife directly affiliated with the trial. Information must take place in an undisturbed room. The subject will be given time to ask questions and allowed sufficient time (minimum 24 hours) to consider the trial before deciding whether to participate.

If subjects so desire, they may make a later appointment with the site investigator after having reviewed the written information about the trial, at which they can meet and discuss participation in the trial. Such a meeting must take place in an undisturbed room and the subject may bring a family member or friend to aid the decision-making. After this meeting, the subject may deliberate on trial participation for up to seven days.

The subjects will be informed of any potential risks associated with the trial.

It is the responsibility of the principal investigator or a sub-investigator to obtain the written informed consent from the subject.

After completion of trial, all participating subjects will be informed of the overall results. Information of individual data and the interpretation hereof will be provided by the investigator. The individual subject's right not to know of own data will be respected.

10.4 Future contact

When subjects are asked to consent to participation in the trial, they will be asked specifically if they can accept possible future contact for the purpose of further research regarding HG. The answer to this question will be recorded on the informed consent form as well as on the e-CRF. Subjects will be able to participate in the trial without giving consent to future contact and they can withdraw their consent at any time.

10.5 Consent for long-term storage of blood samples in a biobank

Subjects will also be asked specifically if they can accept the storage of their samples within a biobank. The answer to this question will be recorded on the informed consent form as well as on the e-CRF. Subjects will be able to participate in the trial without giving consent to long-term storage of blood samples. Subjects may withdraw this consent at any time, and any samples stored in the biobank will then be destroyed.

10.6 Access the offspring's medical journal

In order to register possible congenital malformations and/or hospitalizations of the offspring during the first month after delivery we will ask consent from both parents (forældremyndighedsinnehaver(e)) to access the offspring's medical journal. Access to the offspring's medical journal is solely a safety measure and there will be no intervention on the newborn.

If the co-parent is present at screening or trial visits he/she will be informed verbally and in writing then and there. If the co-parent is not present, the trial subject will be asked if there is a future co-parent and if confirmatory, written information on the trial may be given to the trial subject who can pass it on to the co-parent. The co-parent will be offered to make an appointment with the site investigator after having reviewed the written information on the trial. Such a meeting must take place in an undisturbed room. If the co-parent prefers

CONFIDENTIAL

verbal information on the trial may be given over the phone. The co-parent will be given time to ask questions and allowed sufficient time (minimum 24 hours) to consider whether to consent.

The co-parent may sign the consent form at home and it may be brought to the trial personnel by the trial subject.

10.7 Subject ID number

All subjects enrolled must be identifiable throughout the trial. This will be done by using subject number allocated to the subject at Visit 1 (the screening visit).

10.8 Demography

The following data will be recorded directly in REDCap:

- Date of birth
- Phone number
- E-mail address
- Occupation
- Pre-pregnancy weight
- Gestational age
- Parity
- Possible previous NVP or HG
- Date of initiation of current hospital contact
- PUQE-24 score leading up to current hospital contact

10.9 Medical history and concomitant disease

Medical history is a medical event that the subject has experienced in the past. Only medical history considered relevant by the Investigator should be reported.

Concomitant disease is any illness that is present at the start of the trial (i.e. at the screening visit or found as a result of the screening procedure)

This will be recorded directly in the e-CRF.

10.10 Concomitant and previous medication

All medication taken during current pregnancy will be recorded, as will concomitant medication. Concomitant medication is any medication, other than trial products, which is taken after signing the Informed Consent.

At each visit the Investigator or delegate should ask the subject about use of concomitant medication including rescue medication. All concomitant medication and changes hereto must be documented in the subject's medical records and directly in the e-CRF.

10.11 Vital signs and weight

Blood pressure (BP) and pulse will be measured after 10 minutes sitting rest twice on the left arm with an automatic device.

Weight and height will be measured according to local procedures.

This will be recorded directly in the e-CRF.

10.12 Physical Examination

A physical examination will be performed by the investigator or a delegate according to local procedures.

CONFIDENTIAL

Significant findings that are present at screening must be recorded as medical history in the e-CRF. Significant findings found at the following visits, which meet the definition of an AE, must be recorded on an AE page in the e-CRF.

10.13 Ultrasound scan

An ultrasound scan will be performed by the investigator or a delegate trained to do so. The purpose of the ultrasound scan is to determine gestational age and confirm singleton pregnancy. If the medical journal holds records that an ultrasound scan has been performed within 4 weeks prior to screening visit, a confirmatory ultrasound is not necessary. The ultrasound confirmed gestational age will be recorded in the e-CRF. It will also be recorded whether it was obtained from the medical journal or recorded directly in the e-CRF based on an ultrasound scan performed by the investigator or a delegate.

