8.1 Randomisation

Subjects will be randomised in a 1:1:1 ratio and stratified by site.

Randomisation will be performed using REDCap to create a numbered randomisation list. After identification of an eligible patient, the subject will be assigned a randomisation number and will subsequently receive trial medication corresponding to the randomisation number.

CONFIDENTIAL

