8.3 Sample Size

The trial is dimensioned to find a difference of 2 in PUQE-24 score change from baseline to Day 2 (short term) and/or from baseline to Day 14(+/-1)(long term) between the mirtazapine group and the placebo group with 80% power based on a standard deviation (SD) of change of PUQE-24 score of 3, a type 1 error rate of 2,5% and 25% drop-out. The reason for the 2,5% type 1 error rate is that we want to test 2 hypotheses; effect of mirtazapine versus placebo short and long term on HG.

Thus, we will have to include 57 subjects in each of the 3 groups, which we round up to 60 subjects, equivalent of 180 subjects all together.

An SD of 3 is a conservative estimate based on the placebo-controlled trial with doxylamine-pyridoxine(39).

9. Trial Products

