8.2 Eligibility

Inclusion criteria:

- Written informed consent obtained before any trial related procedures are performed
- Female age >18 years
- Pregnant woman with gestational age between 5+0 and 11+6
- Nausea and vomiting without other obvious reason
- PUQE-24 score ≥ 13 OR

CONFIDENTIAL

PUQE-24 score ≥ 7 AND

1. weight loss $>5\%$ OR
2. hospitalization due to nausea and vomiting of pregnancy

Compliance with this criterion on any given day within 3 days prior to screening (possibly not compliant with this criterion on day of randomization)

- Singleton pregnancy
- The subject must be willing and able to comply with trial protocol

Exclusion criteria:

- Mola pregnancy, multiple gestation or non-vital pregnancy
- Nausea and vomiting of other aetiology than NVP
- Allergic to selective 5-HT₃-receptor antagonists
- Ongoing treatment with antidepressant medication
- Pre-existing diagnosis of chronic kidney disease, diabetes type 1 or 2, significant cardiac disease (incl. long QT syndrome), epilepsy, HIV. In case of other pre-existing conditions subjects might be excluded based on individual assessment by an MD
- Elevated liver enzymes (ALAT/ASAT >150)
- Elevated creatinine (>100)
- ECG showing long QT-syndrome (QTc >460 msek)
- Alcoholism; subject drinks more than recommended by health authorities
- Not able to take medicine orally
- Not able to understand spoken and written Danish
- Participation in another investigational drug trial within current pregnancy

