8.5 Baseline patient characteristics

Baseline characteristics to be summarized in Table 1:

- History of HG in previous pregnancy
- Maternal age

CONFIDENTIAL

- Weight, kg
- BMI, kg/m²
- Gestational age at randomisation, w+d
- PUQE-24 score at randomisation
- NVPQOL at randomisation
- HELP score at randomisation
- EQ-5D at randomisation
- 7 days PSQI at randomisation

9. Analysis

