9.2 Analysis methods

The primary analysis will consist of a linear mixed effects model taking the full longitudinal design into account. The model will be adjusted for site (categorical variable) due to the stratified design. Subjects will be included in the analysis irrespectively of their adherence to the protocol. The treatment effect for the primary outcome will be presented as the average difference between the mirtazapine and placebo groups in PUQE-24 score change from baseline to day 2 and from baseline to day 14. These comparisons will be based on the standard errors from the linear mixed model. Sensitivity analyses will be performed using multiple imputation where the imputation model will include all available baseline variables.

The statistician performing the analyses will remain blinded until the analyses results are closed.

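### The valid site-only primary model leaves out gestational age at randomisation; prespecifying it by visit is a cheap option whose gain depends on an association that the documents do not give

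*Protocol*

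**What the plan says.** Both documents admit women across almost seven weeks of pregnancy: "Pregnant woman with gestational age between 5+0 and 11+6" (SAP 8.2; Protocol 7.1 has the same range). Gestational age is fixed by ultrasound, either at screening or from a scan in the medical record from the previous four weeks, and Protocol 10.13 adds: "The ultrasound confirmed gestational age will be recorded in the e-CRF". SAP 8.5 lists it for Table 1 as "Gestational age at randomisation, w+d". It is therefore a known pre-randomisation value for every woman.

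The design does not balance it by stratification: "Subjects will be randomised in a 1:1:1 ratio and stratified by site" (Protocol 8.1; SAP 6.2 agrees).

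SAP 9.2 describes the analysis thus: "The primary analysis will consist of a linear mixed effects model taking the full longitudinal design into account". It then names one covariate: "The model will be adjusted for site (categorical variable) due to the stratified design". Protocol 13 says the same. Other baseline variables appear in one place only, the sensitivity analysis: "Sensitivity analyses will be performed using multiple imputation where the imputation model will include all available baseline variables". Gestational age thus informs the imputation model, but not the primary contrast or its standard error.

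**The concern.** A woman who enters at 5+0 reaches Day 14 at 7+0; one who enters at 11+6 reaches it at 13+6. If the change in PUQE-24 over those two weeks depends on where in pregnancy a woman starts, that dependence now sits in the residual variance of the Day 14 comparison. Adjusting for a prognostic value measured before randomisation would take it out, without changing what is estimated.

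Only dependence of the change matters. If gestational age shifts the level of PUQE-24 equally at baseline and at Day 14, it already drops out of the contrast.

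What is at stake is precision on a co-primary endpoint with a thin power margin, and the ability to settle the covariate in advance, so that nobody has to decide after Table 1 has shown an imbalance.

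**Working it through.** **Inputs.** Difference 2, SD of change 3, type 1 error rate 2.5% per co-primary endpoint, 80% power, 25% drop-out, 57 per group rounded up to 60 (Protocol 8.3, SAP 6.4). Two-sided test (SAP 6.5). Entry range 35 to 83 days.

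**1. The plan's own sample size.** Normal approximation: n = 2 × 3² × (2.2414 + 0.8416)² / 2² = 42.8 per arm. Then 42.8 / 0.75 = 57.0. The stated 57 reproduces, and it relies on no covariate adjustment.

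**2. Power as planned.** Evaluable per arm: 60 × 0.75 = 45. SE of the difference = 3 × √(2/45) = 0.632. Noncentral-t power with 88 degrees of freedom is 80.9% (the normal approximation gives 82.1%). The noncentral-t figure is used below.

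**3. Power with gestational age added.** Let R² be the share of the variance of the Day 14 change that gestational age explains. The documents give no value, so a range is assumed. The residual SD is 3 × √(1 − R²). Estimating one slope from the two compared arms (N = 90) inflates the variance by 1 + 1/(90 − 2 − 1 − 1) = 1 + 1/86 = 1.0116. So SE = 0.632 × √[(1 − R²) × 1.0116], with 87 degrees of freedom.

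| R² (assumed) | Power, no charge for the parameter | SE, net | Power, net |
|---|---|---|---|
| 0% | 80.9% | 0.636 | 80.4% |
| 2% | 81.8% | 0.630 | 81.3% |
| 5% | 83.1% | 0.620 | 82.6% |
| 10% | 85.2% | 0.604 | 84.7% |
| 20% | 89.3% | 0.569 | 88.9% |

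**4. Break-even.** (1 − R²) × 1.0116 = 1 gives R² = 1.1%, a correlation of about 0.11.

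**5. What an R² means in points per week.** Assume uniform entry over 48 days (6.86 weeks), so the SD is 6.86/√12 = 1.98 weeks. A slope of 0.25 PUQE points of Day 14 change per week gives R² = (0.25 × 1.98/3)² = 2.7%. A slope of 0.5 gives (0.5 × 1.98/3)² = 10.9%. Both slopes are assumptions.

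**6. Chance imbalance.** Under the same assumptions the difference in mean gestational age between arms has an SE of 1.98 × √(2/45) = 0.42 week. At 0.5 points per week that is 0.21 points. This is already part of the unadjusted SE: 0.632² = 0.400, and 0.21² + 0.597² = 0.044 + 0.356 = 0.400. It is the R² of step 5 seen from another side, not a further loss.

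**The case against.** The strongest reply is that nothing is wrong. A site-adjusted mixed model in a randomised trial gives a valid contrast, site is the stratification factor, and the unadjusted power already exceeds 80%. All of this stands.

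Second, the gain is speculative. No section links PUQE-24 change to gestational age, SAP 8.5 lists nine other baseline items that could equally be proposed, and an uninformative covariate costs precision. This also stands, which is why the table starts at zero. The cost is small for one linear term and would be smaller if all three arms shared the slope. With daily scores and categorical time, a linear term by visit adds up to 14 coefficients, but each comparison rests mainly on the coefficient for its own day. A quadratic term has no support in the documents. It would lower power to about 79.9% at R² = 0 and give 82.1% at R² = 5%.

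Three stronger readings are tempting and are not supported:
- **That a certain or free gain is being given up.** The association is unknown and the extra parameter has a price.
- **That chance imbalance in gestational age biases the result.** Step 6 shows that it is covered by the stated standard error and type 1 error rate.
- **That the primary model is exposed to drop-out related to gestational age.** No passage links the two. The mixed model conditions on the observed PUQE-24 series, and the planned imputation, which uses all available baseline variables, assesses the remainder (SAP 9.2 and 9.3).

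**Conclusion.** The point holds as a low-cost improvement to a valid analysis. The plan leaves out of its primary model a baseline value that every woman has, over a wide entry range, and that is not a stratification factor. A single linear term by visit costs about half a power point if gestational age is unrelated to the Day 14 change. It breaks even at about 1% of variance explained, and it adds about 1.7 points at 5%, 3.8 points at 10% and 8 points at 20%.

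These figures rest on 45 evaluable women per arm, a two-sample approximation to the mixed model, the plan's SD of 3, and an assumed R². The Day 2 endpoint follows the same arithmetic with its own, equally unknown, R². A reader might infer that the site-only result would be wrong or underpowered; the documents support neither.

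**What to change.** In SAP 9.2 and Protocol 13, add gestational age at randomisation (weeks, linear) with its interaction with visit to the primary mixed model, and report the site-only model as a sensitivity analysis. The interaction must be stated, because a main effect constant over time would cancel from both co-primary contrasts and gain nothing.

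The change should be made before the randomisation code is added to the cleaned dataset, the point by which Protocol 13 requires the SAP to be accepted. It costs one sentence in each document, no new data, and one extra coefficient per post-baseline visit. If the sponsor has external or blinded pooled evidence that the association is negligible, recording that reason and keeping the site-only model would be an adequate answer.
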